3.1. Overview

Prospective, multicenter, observational cohort study comparing short-term PROs measured with the HM-PRO between two exposure groups: patients undergoing allogeneic stem cell transplantation (allo-SCT) and patients receiving CAR-T cell therapy. Patients will be enrolled at hospital admission for the index inpatient procedure and followed through the inpatient stay (admission → discharge). The study is non-randomized and designed to describe trajectories of symptoms and HRQoL and to estimate the between-group difference in deterioration of HM-PRO scores (primary estimand: mean difference in change score, CAR-T vs allo-SCT).

3.2 Setting:

Two tertiary care hospitals in Rome, Italy, with active allo-SCT and CAR-T in patient programs; multicenter to improve generalizability.

3.2 Duration:

1 year enrollment, participation from hospital admission to discharge (maximum 3 months).

4. Population

One hundred and sixty-two adults (≥ 18 years) with a hematologic malignancy admitted for either (a) allo-SCT (N=81) or (b) CAR-T cell therapy (N=81).

4.1 Inclusion Criteria:

- Age ≥ 18 years
- Diagnosed with a hematologic malignancy (e.g., leukemia, lymphoma, multiple myeloma)
- Undergoing either allogeneic SCT or CAR-T therapy
- Able and willing to provide written informed consent
- Sufficient Italian proficiency to complete the HM-PRO
- Signed informed consent

4.2 Exclusion Criteria:

- Cognitive or physical impairments that preclude the ability to complete questionnaires
- Estimated life expectancy < 7 days at the time of admission

5. Assessment Schedule

Patient-reported outcomes will be collected using the HM-PRO instrument at the following time points:

- T1: Hospital admission
- T2: Day of infusion (CAR-T or stem cell infusion)
- T3: Day 3 post-infusion
- T4: Day 10 post-infusion
- T5: Day of hospital discharge

6. Collected Variables

Demographics:

- Age, Gender, Education level, occupation, civil status

Clinical Variables:

- Comorbidities, Disease type, Disease status (remission/progression), Line of treatment

Laboratory:

- Full blood counts

Treatment:

- CAR-T or allo-SCT treatment details, including conditioning regimen and product specifics

Adverse Events:

- Documented using CTCAE criteria, including:
 - Mucositis, Infections, GvHD, CRS, ICANS

Patient-Reported Outcomes:

- HM-PRO (Impact Scale, Symptoms Scale)

7. Endpoints

Primary Endpoint:

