- Difference in HM-PRO total and domain scores between allo-SCT and CAR-T groups at each time point (T1–T5)

Secondary Endpoints:

- Change in HM-PRO scores over time within each group
- Comparison of PROs by disease status and treatment line
- Frequency and severity of adverse events and correlation with PRO data

8. Statistical Analysis

- All analyses will be performed using two-sided tests with a nominal significance level of $\alpha = 0.05$ unless otherwise stated. Estimates will be reported with 95% confidence intervals.

Primary analysis population include all enrolled participants with at least one post-baseline HM-PRO assessment (intention-to-observe principle).

- Baseline demographic and clinical variables will be summarized by treatment group (allo-SCT vs CAR-T).

- **Continuous variables:** mean (SD) and median (IQR) as appropriate.
- **Categorical variables:** counts and percentages.
- Between-group baseline comparisons will be descriptive (t-tests/Wilcoxon tests or chi-square/Fisher exact tests) to display balance; inferential testing of baseline covariates is not the primary focus. A baseline table will be produced.

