- Exploratory subgroup analyses will be performed for: disease type (AML vs lymphoma vs myeloma), disease status (remission vs progression), age strata, and treatment line. Each subgroup analysis will include a formal **interaction test** (group \times subgroup) within the primary model rather than separate stratified unadjusted tests. Subgroup results are exploratory and interpreted cautiously.

Correlation / association between adverse events and PROs

- **Correlation analyses:** relationship between AE burden (grade or counts) and HM-PRO scores will be examined using Spearman's rank correlation (for ordinal AE grades) or Pearson correlation if assumptions hold.
- **Regression analyses:** to examine whether specific AEs (e.g., CRS, ICANS, mucositis, infections, GvHD) are associated with concurrent or subsequent HM-PRO scores, include AE indicators or graded severity as fixed effects in the mixed model (time-varying covariates). Logistic or Poisson regression (or negative binomial) may be used where appropriate (e.g., modelling probability of clinically meaningful deterioration, or AE counts). Report adjusted effect estimates (e.g., mean differences, odds ratios, incidence rate ratios) with 95% CIs.

- Pre-specify temporal directionality in the SAP (e.g., whether AEs occurring before an HM-PRO assessment are considered predictors).

Handling of missing data

- **Item-level HM-PRO missingness:** per the HM-PRO scoring manual, **missing item responses will not be substituted**; scores will be calculated according to the instrument's guidance.
- **Missing assessments / visit-level missingness:** for missing entire HM-PRO assessments (e.g., missed T2, T3, T4 or T5), the primary approach will be **multiple imputation by chained equations (MICE)** under a missing at random (MAR) assumption. Imputation models will include baseline and post-baseline HM-PRO items/scores, demographic and clinical covariates, laboratory markers, site, and indicators predictive of missingness. We will perform at least $m = 20$ imputations (or more if fraction of missing information is high) and combine estimates by Rubin's rules.
- **Sensitivity analyses:** compare results from: complete-case analysis, multiple imputation, and worst-case / tipping-point analyses to assess robustness to missing not at random (MNAR) mechanisms. The SAP will detail variables included in imputation models and diagnostics for imputation quality.

Multiplicity and inference

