9.3 Patient-reported outcomes

The **HM-PRO instrument**, a validated PRO tool for patients with hematological malignancies, will be used to assess symptom burden and health-related quality of life (HRQoL). HM-PRO will be self-administered in paper format by patients at standardized time points during hospitalization:

- **T1:** Hospital admission (baseline)
- **T2:** Day of infusion (CAR-T or stem cell infusion)
- **T3:** Day 3 post-infusion
- **T4:** Day 10 post-infusion
- **T5:** Day of hospital discharge

Study staff will facilitate administration of the instrument and verify completeness of responses. Where patients are unable to self-complete due to temporary health-related limitations, assistance will be provided in accordance with HM-PRO guidance to preserve data validity. The completed questionnaires will be scanned and uploaded into the REDCap system to ensure secure storage and source documentation.

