9.4 Collected variables

Demographics

- Age
- Gender
- Education level
- Occupation
- Civil status

Clinical variables

- Comorbidities (documented at admission)
- Disease type (e.g., AML, lymphoma, myeloma)
- Disease status (remission vs progression)
- Line of treatment (first-line vs subsequent lines)

Laboratory

- Full blood counts at baseline and as per standard of care during hospitalization

Treatment-related data

- Treatment modality (CAR-T or allo-SCT)
- Conditioning regimen details
- Product specifics (CAR-T product characteristics or stem cell source/donor type)

Adverse events

Adverse events will be systematically captured and graded according to **Common Terminology Criteria for Adverse Events (CTCAE, version 5.0)**. The following specific toxicities of interest will be documented:

- Mucositis
- Infections
- Graft-versus-host disease (GvHD; allo-SCT group only)
- Cytokine release syndrome (CRS; CAR-T group only)
- Immune effector cell-associated neurotoxicity syndrome (ICANS; CAR-T group only)

10. Schedule of Procedures

Procedure / Assessment	T1: Admission	T2: Infusion	T3: Day 3 Post-Infusion	T4: Day 10 Post-Infusion	T5: Discharge
Informed consent	✓	-	-	-	-
Eligibility check	✓	-	-	-	-
Demographics	✓	-	-	-	-
Clinical variables (comorbidities, disease type, status, line of treatment)	✓	-	-	-	-
Laboratory tests (full blood counts)	✓ (baseline)	As per SOC	As per SOC	As per SOC	As per SOC
Treatment details (conditioning regimen, product specifics)	-	✓	-	-	-

Procedure / Assessment	T1: Admission	T2: Infusion	T3: Day 3 Post-Infusion	T4: Day 10 Post-Infusion	T5: Discharge
Adverse events (CTCAE vX.X)	-	✓ (from infusion)	✓	✓	✓
HM-PRO questionnaire	✓	✓	✓	✓	✓
Questionnaire scan & upload to REDCap	✓	✓	✓	✓	✓

✓ = performed

SOC = standard of care

11. Dissemination of Results

Study results will be submitted for presentation at scientific conferences and for publication in peer-reviewed journals. All publications will maintain patient confidentiality and comply with authorship standards.

12. Funding and Conflicts of Interest

This study is sponsored by QOL-ONE Research Association. No conflicts of interest are declared by the principal investigators or collaborators.

13. References

2. Neelapu SS, et al. Chimeric antigen receptor T-cell therapy — assessment and management of toxicities. *Nat Rev Clin Oncol.* 2018.

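### Adverse event capture starts at infusion, so the HM-PRO change from admission to infusion has no scheduled adverse event data beside it

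*Protocol*

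**What the plan says.** Section 3.1 has patients enrolled at admission and "followed through the inpatient stay (admission → discharge". Section 9.3 makes T1 the baseline questionnaire and T2 the one on the day of infusion, and Section 10 ticks HM-PRO at all five time points.

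The adverse event row of Section 10 has a dash at T1, a tick at T2 qualified by "from infusion", and ticks at T3, T4 and T5. Sections 6 and 9.4 name the toxicities of interest (mucositis, infections, GvHD, CRS, ICANS). Section 9.4 adds that capture is systematic and CTCAE-graded. Neither section gives a start date, so the schedule alone sets the window.

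Section 7 lists as a secondary endpoint "Frequency and severity of adverse events and correlation with PRO data". Section 8.1 examines that association by correlation, and by entering adverse events as time-varying covariates for concurrent or later HM-PRO scores in the mixed model. It leaves one choice to the SAP: "whether AEs occurring before an HM-PRO assessment are considered predictors".

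**The concern.** The questionnaire and the adverse event record cover different periods. HM-PRO runs over the whole stay, and adverse event capture runs from infusion onwards. Any change in HM-PRO between admission and infusion enters the longitudinal model, but toxicity arising in that same interval has no scheduled record.

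Two uses of the data are exposed. The first is the count and severity of adverse events. Read as a description of the hospital stay, it will be too low, and the shortfall may differ between groups if one group spends longer in hospital before infusion or has more toxicity there. The second is the adverse event–PRO association, which has no preceding adverse event data with which to explain the T2 score.

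The SAP can decide how recorded events are used. It cannot recover events that were never entered on the eCRF, so the window has to be settled in the protocol.

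**Working it through.** The plan states no figure on this point, so the check sets the two schedule rows side by side and counts.

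| | T1 admission | T2 infusion | T3 day 3 | T4 day 10 | T5 discharge |
|---|---|---|---|---|---|
| HM-PRO (Sections 9.3, 10) | yes | yes | yes | yes | yes |
| Adverse events (Section 10) | no | yes, starting at infusion | yes | yes | yes |

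**Intervals.** Five assessments give 5 − 1 = 4 intervals: T1–T2, T2–T3, T3–T4 and T4–T5. Adverse event capture covers the last three. T1–T2 is uncovered, which is 1 of 4.

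**Questionnaires.** The planned enrolment is 162 (Section 4), with four post-baseline questionnaires each: 162 × 4 = 648 at most. The T2 questionnaires are up to 162 of these, and 162 / 648 = 25%. This is the share of post-baseline scores whose preceding interval lacks adverse event capture. It is not a measure of bias.

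**What is lost, by type of event before infusion.**
- Begins and resolves between T1 and infusion: not scheduled for capture at all.
- Begins before infusion and is still present then: can be noted at T2 and used as concurrent with the T2 score, but its onset and earlier course are not scheduled for capture.
- Begins on or after infusion: captured.

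**Which toxicities are at stake.** Section 9.4 ties GvHD to the allo-SCT group, and CRS and ICANS to the CAR-T group. These three follow the infused product, so a window opening at infusion does not miss them. That leaves mucositis and infections, 2 of the 5 listed.

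**Other data that might fill the gap.** Section 10 records conditioning regimen details at T2, and blood counts at baseline and then as per standard of care. Neither records mucositis or infection before infusion.

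**Which analyses are touched.** The base mixed model and the ANCOVA in Section 8.1 contain no adverse event term, so the primary HM-PRO comparison does not depend on this window. The adverse event frequencies and the adverse event–PRO correlations and regressions do.

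**The case against.** A window that opens at the index infusion is coherent and uniform across the two groups, and the protocol nowhere promises an adverse event predictor for every questionnaire. The SAP, which is not shown, could confine the adverse event–PRO models to T3–T5 and so avoid misclassifying anyone at T2. This stands as far as it goes: restricting the models avoids a wrong analysis, but it leaves the pre-infusion events uncounted.

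Some stronger readings are tempting, and the protocol does not support them:
- *Pre-infusion toxicity is never recorded.* T2 is a ticked adverse event assessment, so an event still present at infusion can be noted there.
- *The adverse event predictor at T2 is zero by design, so every patient with an earlier event is misclassified.* Section 8.1 allows concurrent events, and no section says that an unobserved interval is coded as event-free.
- *Conditioning falls wholly between T1 and T2, in hospital.* The protocol gives no conditioning dates and no admission-to-infusion interval for either group. Recording the regimen at T2 is compatible with that reading but does not establish it.
- *A known proportion of patients is affected.* The protocol gives no rate of pre-infusion events and nothing from which to derive one.
- *The adverse event coefficients are seriously biased towards zero.* If the missed events were treated as absent, some dilution is plausible. It is probably small: only the T2 records are directly affected, and the group × time terms absorb average shifts at T2.

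**Conclusion.** The mismatch is real and follows directly from Section 10: one of four intervals has a measured HM-PRO change and no scheduled adverse event capture. Two consequences hold. Mucositis and infection frequency over the stay is undercounted, and the T1–T2 change has no adverse event data behind it in the secondary adverse event–PRO analysis.

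The size of the undercount cannot be calculated from the protocol. It depends on the length of the pre-infusion stay and on the event rate within it, and neither is given. Whether it differs between groups rests on the same missing facts, so an unequal undercount is a possibility and not a finding.

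This is a minor issue. It concerns a secondary endpoint, in a plan whose Section 8.1 describes its multiple secondary endpoints as exploratory. It is worth correcting because the correction is cheap and cannot be made by analysis afterwards.

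**What to change.** In Section 10, start adverse event capture at T1 in both groups, and take onset date, end date and grade from the chart. State the same window in Section 9.4. In the adverse event–PRO models, use events with onset between T1 and T2 as predictors of the T2 score.

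The cost is a few more days of chart abstraction per patient and added date fields on the eCRF. No visit, procedure or questionnaire is added, and patient care does not change.

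If capture is not extended, state in Sections 7 and 8.1 that adverse event frequencies are post-infusion only, and restrict the adverse event–PRO models to T3–T5. That costs nothing in data collection, but it gives up any adverse event explanation of the T1–T2 change.
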